- In this epistemological position this study is best regarded as a well powered but exploratory test of the methods contributing a substantial, but tentative, body of new knowledge.
- The data are largely quantitative and the approach largely statistical within a statistical tradition of (Abelson, 1995; Spiegelhalter, 2019). We also follow the principles of (Wagenmakers et al., 2021, 'Seven steps toward more transparency in statistical practice') specifically:
 - (1) visualizing data;
 - (2) quantifying inferential uncertainty;
 - (3) assessing data preprocessing choices;
 - (4) reporting multiple models;
 - (6) interpreting results modestly; and
 - (7) sharing data and code.

Their fifth step, involving multiple analysts is beyond our resources but we welcome offers from others to reanalyse our data, ideally in collaboration but of course our making the data and code available publicly makes it possible for anyone to reanalyse our data. Particular reference to these steps are noted against particular aspects of our analyses below.

- Some elements are frankly exploratory and pathfinding: mainly the quantitative and qualitative data from the "What's Going On?" (WGO, see registration and protocol) and their relationship with other variables. We are particularly careful to present these as such and not to overclaim for them (Wagenmakers et al., 2021, steps 1, 2, 4 and 6).
- In general the statistical position is descriptive and based on estimation rather than formal null hypothesis significance testing (NHST) and we use confidence intervals (CIs) to understand the probable impacts of sample size on precision of estimation of population parameters. Where statistical tests are used, they aim to give a pragmatic indication that non-random effects exist, not to give strong assertions that "x is a statistically significant effect" but, with the CIs, to help disentangle seemingly systematic effects from random ones. (Wagenmakers et al., 2021, steps 2, and 6)
- We recognise that the sample is not a random one so caution will be exercised in any generalisations to the wider population (Wagenmakers et al., 2021, steps 2 and 6).
- We recognise that there will be incomplete responding and that a small proportion of participants may cross from one baseline group, i.e. students or non-students, to the other group. The impacts of these issues will be explored (Wagenmakers et al., 2021, steps 2, 3, 4 and 6).

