To understand more of the levels of distress of emerging adults in Ecuador over a one year period.
 - Specific questions:
 - i. What, for the purposes of comparisons between people, do the baseline data say about the psychometric quality of the two multi-item measures (CORE-OM, EQ-5D-3L; see registration)?
 - ii. What do the change data say about the psychometric quality of the two multi-item measures as measures of change and particularly of intra-individual change?

This is not the same issue as (i) though traditional psychometric methods tend to be presented as if it were the same so it may be wise to expand this distinction here.

Traditional psychometric methods are designed to address differences between individuals and when considered to address our next question (iii below) such methods are appropriate. However, in order to assess the psychometric qualities of the measures *for measurement of within-participant change* traditional methods must axiomatically assume that individual change has the same covariance structure as the covariance structure of score comparisons between individuals.

In fact there is no reason to believe that this will be true for complex psychological variables like well-being or quality of life. For such variables it

is more plausible that there are within-participant patterns of change across multiple items just as it is plausible that temporal variation is not the same for all individuals. See (Molenaar, 2004) for a trenchant exposition of the issues.

For example it may be that some participants have fluctuating problems with social functioning while others, say, struggle with confidence but not social functioning. If this is true over the year, then the covariance structure of change across CORE-OM items within the person struggling with social functioning would be different from that of the person struggling with confidence and neither need show an item change covariance matrix resembling the item score covariance matrix across all participants at baseline. However, as long as sufficient items are affected for each of those participants, the CORE-OM-NR would still be a useful change measure for each participant and that utility would be unrelated to the baseline conventional reliability of the measure.

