- However, as noted above, the CTT assumption that the within-participant change measurement model is the same as the between-individual model is highly implausible for mental health change measures. If that is accepted and that constraint abandoned these above checks on change measurement quality from within CTT cease to be definitive and could miss situations in which measures are useful measures of within-participant change, change which might be different across the items of the measure between individuals and having no shared factor structure between individuals. In that situation, an extreme deviation from the CTT model, change recorded across the items within each individual might still be usable reliable and valid indicators of within-

participant psychological change.

Abandoning the CTT model in this way still allows two simple explorations which can help understand more about the quality of measures as measures of within-participant change. These are currently new methods and seven occasions provide only minimal power for the second method but these will be used as part of a wider project of inspection of the psychometrics of individual change.

- A measure can be useful as an aggregate measure of individual change if within-participant change is correlated across multiple items *but the correlated items being different for different individuals but not unique to individuals*. If this is the case, then Cronbach's alpha from item score changes (as opposed to scores at a point in time) is an indicator that, despite differences in the structure of change by individual, within-participant change is being indexed across items. This can be applied for any of the up to 21 score pairs.

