- That still looks for some shared change across individuals. Dropping that measurement expectation entirely, but transferring CTT to within-participant change allows computation of the alpha for change within-participant. The parametric 95% confidence interval for an observed alpha of .6 from $n = 7$ (i.e. all seven occasions) for 28 items (the CORE-OM-NR) is from 0.0 to .92, i.e. reaching a point at which a model of no reliability of within-participant change is looking implausible. We will report within-participant Cronbach alpha values for all participants with full item data from all seven occasions for the CORE-OM-NR score and also, separately, for those with fewer occasions. Where the parametric lower confidence interval exceeds zero the first principal components of the within-participant PCA will be inspected and it is expected that these will be markedly different for different participants with these high personal change Cronbach alpha values, illustrating that within-participant change on a measure like the CORE-OM can be reliable be markedly different in structure between individuals. This can also be done for all 34 items making up the full CORE-OM. For the shorter scales/scores such as the EQ-5D-3L or the domain scores of the CORE-OM the number of items are not sufficient to give any reasonable power to find internal reliability with only seven measurement occasions and this model will not be explored for the shorter scales/scores.
- Does baseline group, student vs. non-student, appear to relate to change on the dependent variables? All change scores and distributions will be plotted allowing both individual values and central location statistics with CIs to be seen.
All analyses will be firstly "intention to treat" (ITT), i.e. by baseline group.

However, many students will also hold jobs. How much this relates to scores on dependent variables will be explored by analysing with these "students-who-also-hold-jobs" as a group and by reclassifying them into the non-student group. These additional explorations will explore the sensitivity of any relationships to baseline group to these real world complexities.

It seems plausible that these "students-who-also-hold-jobs" are sufficiently different from either the students without any outside course employment or from the young people with jobs and no university study that this issue may need to be considered alongside the simple ITT analyses.

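### Visible differences between participants' first principal components (28 items, seven occasions) cannot by themselves illustrate person-specific structure, because a shared structure of low to moderate strength looks the same

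*SAP*

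**What the plan says.** In the SAP's Analyses section, under Change analyses, Cronbach's alpha is computed within each participant from the 28 CORE-OM-NR items over seven occasions, "and also, separately, for those with fewer occasions". Where the lower confidence limit of that alpha is above zero, "the first principal components of the within-participant PCA will be inspected". The result is anticipated: "it is expected that these will be markedly different for different participants with these high personal change Cronbach alpha values". So is its meaning: "illustrating that within-participant change on a measure like the CORE-OM can be reliable be markedly different in structure between individuals". A 34-item version is allowed ("This can also be done for all 34 items making up the full CORE-OM"). The SAP does not say what counts as a marked difference, how similarity is measured, or how different the components would look if everyone shared one structure.

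The one caveat comes shortly before: the methods are new, and "seven occasions provide only minimal power for the second method". The motivation is in specific question ii, where for two people struggling with different things "neither need show an item change covariance matrix resembling the item score covariance matrix across all participants at baseline". The section on epistemological and methodological position says that tests and confidence intervals are there "to help disentangle seemingly systematic effects from random ones".

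**The concern.** Seven person-centred rows give a matrix of rank at most 6, from which 28 loadings are estimated. Loadings estimated this way can differ widely between two people by chance alone. If they do so even when the underlying structure is identical, the observation the SAP expects does not favour one explanation over the other.

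The caveat about minimal power does not cover this. Low power warns that a real effect may be missed; here few occasions can create the expected pattern when it is absent. Person-specific covariance of change is the reason given for question ii, and this step is where it is to be illustrated, so readers could take sampling error for support of that idea.

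**Working it through.** **1. The SAP's own figure.** Inputs from the SAP: alpha .6, n = 7 occasions, k = 28 items, 95% interval. Feldt's limits are 1 − (1 − alpha) × F, with F on n − 1 = 6 and (n − 1)(k − 1) = 162 degrees of freedom.
- Lower: 1 − 0.4 × 2.487 = 0.005
- Upper: 1 − 0.4 × 0.2045 = 0.918

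This reproduces the stated 0.0 to .92. The SAP's arithmetic is right.

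**2. The selection rule.** The lower limit exceeds zero when alpha > 1 − 1/2.487 = 0.598 (0.596 for 34 items).

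**3. What that alpha implies.** With equal item variances, the mean inter-item correlation is rho = alpha / (k − (k − 1) × alpha).
- Alpha .60: .60 / (28 − 16.2) = 0.05
- Alpha .92: .92 / (28 − 24.84) = 0.29

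With 28 items, an alpha that clears the rule can rest on very weak correlations. The SAP's worked interval runs up to a rho of about .29.

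**4. Simulation under one shared structure.** Assumptions: one factor, equal loadings, continuous items, independent occasions, complete data. There were 14,000 simulated participants per setting. The alpha rule was applied, up to 5,000 who passed were kept, and absolute congruence was taken between the first components of independent pairs. The SAP gives no within-person correlations, so a range is shown. Entries are median congruence, covariance / correlation PCA.

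| rho | passing the rule (28 items) | 28 items | 34 items |
|---|---|---|---|
| .05 | 42% | 0.24 / 0.22 | 0.21 / 0.19 |
| .10 | 73% | 0.33 / 0.33 | 0.31 / 0.30 |
| .20 | 93% | 0.53 / 0.55 | 0.52 / 0.55 |
| .30 | 98% | 0.66 / 0.72 | 0.67 / 0.72 |
| .50 | not tabulated | 0.83 / 0.91 | 0.83 / 0.90 |
| .70 | not tabulated | 0.92 / 0.98 | 0.92 / 0.98 |

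Single pairs vary more: the 10th to 90th percentiles (28 items, correlation PCA) are 0.19–0.77 at rho .20 and 0.40–0.88 at rho .30. A separate simulation of the 28-item case gave medians (covariance PCA) of 0.24, 0.34, 0.53, 0.66, 0.83 and 0.92 at the same six values of rho. There, with equal shared loadings, the seven highest-loading items of two people overlapped by about 1.75 of 7, which is the chance value (7 × 7/28 = 1.75).

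**5. Variations.**
- *Five-category items* (correlation PCA; rho .20, .30, .50): four assumed cut-point settings gave 0.34–0.46, 0.44–0.62 and 0.64–0.85. Symmetric cut-points gave 0.52, 0.68 and 0.88. These depend on the setting and are not bounds.
- *Fewer occasions*, if the PCA step extends to them (correlation PCA; 6, 5, 4 occasions): 0.50, 0.44, 0.40 at rho .20 and 0.66, 0.60, 0.52 at rho .30.

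**6. Does a common-structure reference work?** Assumed: 50 selected participants, 30 replicates, correlation PCA, and a reference that keeps each person's own item variances and matches the first component's variance share. Entries are median pairwise congruence, mean (95% range).

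| True situation | Observed | Reference |
|---|---|---|
| Shared, rho .30, residual SDs varying between people | 0.71 (0.66–0.75) | 0.66 (0.61–0.72) |
| Person-specific, loadings .70 / 0 | 0.35 (0.31–0.39) | 0.61 (0.54–0.65) |
| Person-specific, loadings .60 / .15 | 0.42 (0.37–0.46) | 0.51 (0.47–0.58) |
| As above, residual SDs varying | 0.47 (0.43–0.50) | 0.54 (0.49–0.59) |

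A strong person-specific contrast is detected and a weak one is borderline. For the shared data in the first row, covariance PCA with a pooled reference gave 0.41 (0.32–0.48) against 0.63 (0.56–0.68), a false signal. That is why correlation PCA and own variances matter.

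**The case against.** The strongest reply is that the SAP claims little. It inspects and illustrates, attaches no test or decision, calls the methods new, describes the study as exploratory and promises modest interpretation. It argues for person-specific structure on prior grounds, so the idea does not rest on this step. All of that stands and limits the consequence. It does not make an observation informative when both explanations predict it.

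Second, the problem depends on an unknown. At rho .50 to .70 shared components agree well, and at .05 to .10 there is little shared structure to miss. The reported personal alphas would tell readers roughly where the data lie. This also stands, and the point is limited to low-to-moderate correlations for that reason. But the SAP does not make its reading conditional on the alphas being high, and its rule admits values from about 0.6.

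Third, strong person-specific and shared structure do differ in degree (0.35 against 0.61 above). True, but seeing that needs a yardstick, and the SAP has none.

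Fourth, the simulated reference is imperfect: it can sit below the congruence seen under a truly shared structure (0.66 against 0.71), so weak real differences may be missed. That is fair, and the reference is needed only if a structural conclusion is wanted.

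The longitudinal invariance tests and change-score alphas also bear on shared structure, but neither addresses sampling error in an individual's component.

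**Conclusion.** The concern holds. With seven occasions and 28 or 34 items, one structure common to everyone gives a median congruence of roughly 0.2 to 0.7 between selected participants' first components at inter-item correlations of .05 to .30. The alpha rule does not screen these cases out. Inspected differences alone therefore cannot support the reading the SAP fixes in advance. If within-person correlations are about .50 or higher, a shared structure would mostly look shared and the inspection would carry information.

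The size rests on assumed correlations and the simplified model described above; the conclusion does not rest on the five-category results. This should be corrected, but its reach is one exploratory step under question ii. The group comparisons, clinical cut-point rates and life-event analyses are unaffected.

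**What to change.** **Minimum, one sentence in the SAP:** the first components are reported descriptively, and no person-specific structure is inferred from inspected differences alone.

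**If a structural conclusion is wanted:**
- Use correlation PCA and report between-person congruence beside its distribution simulated from one common structure.
- Match the reference on number of occasions, item response scale and alpha rule. Keep each participant's own item variances, and scale the common factor so that the first component's variance share equals the observed share.
- Conclude that structures differ only where observed congruence is clearly below the reference. Otherwise state that seven occasions cannot separate the two explanations. No significance threshold is needed.
- State how items that stay constant over a participant's occasions are handled, since their correlations are undefined, and treat them the same way in the reference. Under the assumed cut-points, 0.0 to 5.5 of 28 items per participant were constant.
- State whether the PCA step extends to participants with fewer than seven occasions; if so, use a reference with the same number.

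**Cost:** a short simulation from each participant's item means and variances, with no new data. The illustration may become inconclusive, and weak person-specific structure may not be separable.

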This raises the question whether there are simple analyses that throw more appropriate light on the psychometrics of using the questionnaires to measure individual change than do the conventional explorations of psychometric quality of multi-item questionnaire measures for cross-sectional comparisons between people. This will be explored (details in the PPDAC "A" section: analyses, below).

- iii. As most existing data on the well-being and mental health problems of this age group are from student samples, a primary focus will be on differences between a student and a non-student sample both at baseline and subsequently through the year.
- iv. How much do scores on the dependent measures (CORE-OM, EQ-5D-3L and EQ-VAS, see registration) vary across the seven time points and is there evidence that the level of variation varies across the sample, i.e. that temporal stability is not a consistent parameter but show strong individual differences? Analyses of the CORE-OM will consider the non-risk and risk scores only (but see "supplementary analyses").
- v. Does baseline group, student vs. non-student, appear to relate to the dependent variables? Do other demographic predictors relate to the dependent variables? Recognising that "the dependent variables" will have temporal variation this will be divided into two sets of analyses:
 - 1. Using baseline scores only
 - 2. Analysing the full change data (more details below):
 - a. Testing for difference in any systematic linear trend over the seven time points.
 - b. Against within-participant SD of the scores.
 - c. Against highest and lowest within-participant difference from baseline.
- vi. What levels of and changes in stressors/life events (LE) do participants report on the novel "What's going on?" (WGO) measure?
- vii. Is there evidence of systematic relationship between stress and dependent variable scores within-participant over time?
- viii. Given the inevitably non-random nature of the sampling creating the dataset this will be compared with the most recently available census data

from Quito for this age group to see how much the sample differs from the census data where comparable variables are present in the census data.

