 - With hindsight and having conducted analyses along these lines we are aware that there are many other ways of exploring these complexities in survey data and would particularly welcome offers from data analysts to explore other methods of exploration of these issues in this baseline dataset.
 - Baseline non-participation will be reported to the extent that the opportunistic recruitment process allows though this can only be in terms of potential number of students who might have opted into the study and then in terms of the numbers who start the online data collection but opt out before giving usable data.
 - For the CORE-OM and EQ-5D-3L internal reliability and factor analysis will be conducted (but not expecting neat factor structures). In addition, convergent validity correlations between the two measures, and with the EQ-VAS, will be reported, as usual with 95% CIs.
 - Distributions of CORE-OM, EQ-5D-3L and EQ-VAS scores and of WGO scores will be reported with CIs for centiles.
 - Baseline associations between those three dependent variables and the WGO scores will be reported with scattergrams and smoothed LOESS

regression lines and CIs.

- **Change analyses**

- Patterns of post-baseline missingness will be reported. These will almost certainly show a preponderance of simple attrition: i.e. increasing non-response in waves 2 to 7, however, other patterns are also likely to be observed. As there are 64 possible further completion patterns (2^6) the missingness will be analysed in terms of simple dichotomy of "all completed" versus "at least one missing" and in terms of the total number of completions (1 to 7). These will be analysed against baseline demographic and dependent variable scores for evidence of any of these variables showing systematic associations with missingness. The associations will be reported testing against an alpha of .01 as in the baseline analyses but also with CIs for the associations.

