Some participants will probably change group during the year though these will probably be less numerous than "students-who-also-hold-jobs". Due to the timing of the data collection, students are probably more likely to terminate their courses during the year than are non-students to start a degree. Here again, sensitivity analyses will be conducted recomputing the analyses (a) omitting participants who change group at any point in the year and (b) omitting only those changing group whose change comes less than half way through the year and (c) reallocating those who change group to the group they fall in for more than half the year. However, the expectation is that the numbers changing group will be small and the impacts on the ITT findings small or negligible.

Recognising that these dependent variables have temporal variation and this variation is likely to be complexly patterned across the entire sample, the following analyses will be reported for the ITT baseline group comparison and the sensitivity analyses noted above.

- Group difference against mean scores across all non-missing scores from all seven occasions. This extends the analyses of baseline group differences and entirely ignores change over time.
- Group difference in linear trend over the time points using multi-level modelling (MLM). This allows a trend to be fitted both as a fixed effect whose interaction with predictors can be tested, i.e. assuming a single within-group population mean, and then also allowing a free effect, i.e. allowing that linear trend against time may vary between individuals. The MLM provides an individual (free) linear slope if scores at least two time points exist. However, sensitivity checks on effects of missingness will be added by restricting to sequentially larger numbers of time points.
- Group differences in within-participant SD of the scores (wpSD).
- Group differences in within-participant score difference from baseline (wpMaxChange).
- Group differences in within-participant score range (wpScoreRange).
- Do other demographic predictors relate to the dependent variables? Same methods as for group differences.

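### The group comparison of person-mean scores over the seven occasions leans towards early waves under the attrition the plan expects, and no attrition-robust level difference is planned beside it

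*SAP*

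**What the plan says.** All of this is in the SAP, section PPDAC approach.

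- **Specific questions, item iii**: "a primary focus will be on differences between a student and a non-student sample both at baseline and subsequently through the year".
- **Change analyses, group comparisons**: the opening item of the list is "Group difference against mean scores across all non-missing scores from all seven occasions". The SAP qualifies it at once: "This extends the analyses of baseline group differences and entirely ignores change over time". The item sets no weighting by wave, no minimum number of waves and no method for missing scores.
- **Next item in that list**: a multi-level model (MLM) aimed at a group difference in slope, with individual slopes allowed to vary. Only here does the SAP state that "sensitivity checks on effects of missingness will be added by restricting to sequentially larger numbers of time points".
- **Change analyses, missingness**: "These will almost certainly show a preponderance of simple attrition", described as "increasing non-response in waves 2 to 7". Completions per person are taken to run from one to seven. Missingness will be tested against baseline demographics and scores. No attrition rate is given.
- **Reuse**: the list also serves the sensitivity analyses on group membership, and the other demographic predictors are to be handled in the same way.

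**The concern.** When drop-out is mostly monotone, a person who completes k waves has a mean over waves 1 to k only. That person counts as much in the group comparison as someone with all seven scores. Averaged over the sample, early waves carry more weight than late ones, by an amount that depends on the attrition pattern.

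This has two consequences. If the gap between groups widens or narrows, the summary is pulled towards its early value, even when drop-out is the same in both groups and unrelated to scores. If both groups drift together but one loses more people, the groups' means cover different parts of the year and a gap appears where none exists.

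At stake is the level part of a comparison the SAP calls a primary focus, and every comparison that reuses the method.

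**Working it through.** **Inputs from the SAP:** seven waves; completions from 1 to 7; mainly simple attrition; an unweighted mean of non-missing scores. The SAP gives no sample size, attrition rate or expected gap for this item, so there is no figure of its own to reproduce. Retention rates and gap shapes below are assumptions.

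**Gap growing from zero.** Let the gap at wave w be D(w−1)/6, so 0 at baseline and D at wave 7. The equal-weight average over seven waves is D/2. A person whose last wave is K contributes an expected D(K−1)/12. The share recovered is therefore

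(E[K]−1)/6.

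With constant retention r per wave and wave-7 retention R, r = R^(1/6) and E[K] = 1 + r + r² + … + r⁶. For R = 70%: r = 0.942, E[K] = 5.90, share = 4.90/6 = 0.82.

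**Gap present at baseline and doubling.** Let it run linearly from g to 2g. The true average is 1.5g, and the share recovered is [1 + (E[K]−1)/12]/1.5. For R = 70%: (1 + 0.408)/1.5 = 0.94.

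| Wave-7 retention | r | E[K] | Share, gap from zero | Loss | Share, gap doubling | Loss |
|---|---|---|---|---|---|---|
| 80% | 0.963 | 6.28 | 0.88 | 12% | 0.96 | 4% |
| 70% | 0.942 | 5.90 | 0.82 | 18% | 0.94 | 6% |
| 50% | 0.891 | 5.08 | 0.68 | 32% | 0.89 | 11% |
| 30% | 0.818 | 4.15 | 0.53 | 47% | 0.84 | 16% |

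**Constant gap.** Every wave carries the same gap, so the share is 1 whatever the retention.

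**No true gap, shared linear trend of T over the year, unequal retention.** The false gap is T(E[K_A]−E[K_B])/12. At 70% versus 50%: (5.90−5.08)/12 = 0.07T. At 70% versus 30%: (5.90−4.15)/12 = 0.15T.

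**Weight on the baseline score.** The average weight is E[1/K]: 1/7 = 0.14 with complete data, 0.23 at 70% retention and 0.30 at 50%.

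**Check of the remedy.** For each retention level, 25 datasets of 600 people were simulated with a true seven-wave average gap of 0.20 (0 at baseline, 0.40 at wave 7), random intercepts and slopes, and drop-out unrelated to scores.

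| Wave-7 retention | Complete data | Raw person mean | MLM averaged over seven waves |
|---|---|---|---|
| 70% | 0.205 | 0.167 | 0.205 |
| 50% | 0.203 | 0.136 | 0.202 |
| 26% | 0.207 | 0.105 | 0.211 |

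The model here used linear time, which matched the simulated truth. The check shows that a mixed model fitted to the available scores recovers the seven-wave average in this setting. It does not test the wave-as-factor form or drop-out that depends on scores.

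**The case against.** The best defence is that the SAP promises little for this item. It says the summary ignores change, never claims an equal-weight seven-wave target, and leaves this item out of the change analyses listed under specific question v. A widening gap is the business of the MLM in the next item, which tests the interaction with time and has a missingness check. The study is described as exploratory and estimation-based, with several models to be reported and the impact of incomplete responding to be explored.

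Much of this stands. A reader might infer that the plan would miss a widening gap; it would not, at least for a linear one. What does not follow is that the level comparison is sound. Ignoring change is harmless only with complete data or a constant gap; otherwise the result depends on change combined with drop-out. The MLM is specified for slope, not level, and its missingness check is not stated for this item.

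Three other stronger readings go beyond the document:

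- **That attrition halves the difference.** This needs no gap at baseline and an average of four completed waves out of seven, since (4−1)/6 = 0.5. That means about 27% still present at wave 7 under constant retention, or half the sample lost straight after baseline. Nothing in the SAP supports either.
- **That the summary largely repeats the baseline comparison.** Even with completions spread evenly over 1 to 7, the baseline weight is (1 + 1/2 + … + 1/7)/7 = 0.37, so 63% of the weight is post-baseline.
- **That drop-out following earlier scores causes material bias.** The SAP gives neither a between-wave correlation nor a drop-out pattern from which to size this.

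The wording could also mean one pooled mean over all observations. The tilt is then milder: at 27% retention the share recovered is about 0.72 rather than 0.50.

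**Conclusion.** The concern holds in a limited form. On its natural reading, the planned mean-score comparison is tilted towards early waves by the attrition the SAP itself expects. It is not the seven-occasion level difference if the gap changes over the year, and it can show a false gap if retention differs between groups that share a trend. Nothing else in the plan supplies a level difference protected against this.

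The size cannot be fixed from the document. Under the assumed patterns it runs from nothing (constant gap), through modest (a gap that doubles), to roughly an eighth to nearly a half of the true average (a gap starting at zero, retention 80% down to 30%). These figures assume linear change and constant per-wave retention, equal in both groups except in the shared-trend case. The change should be made because the comparison serves a primary focus and is reused for other predictors; it does not undermine the trend analysis.

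**What to change.** Amend the mean-score item as follows:

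1. Estimate the level difference from a mixed model on all available scores, with group, wave as a factor, group by wave, and participant random effects.
2. Report the group difference averaged with equal weight over the seven waves, with a 95% CI, as the main level comparison.
3. Keep the raw person-mean comparison beside it, labelled descriptive, and apply to it the check that restricts to larger numbers of completed waves.
4. Carry the same wording to the group-membership sensitivity analyses and the other demographic predictors.

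The cost is a few lines of text and slightly more analysis; no new data are needed, and the model class is already planned. The SAP dates this version before any inspection of the change data and allows marked amendments, so at that date the change could still be pre-specified. The price is reliance on a correctly specified model and on scores being missing at random, which should be stated with the result.
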